DAIT-COVID-19-001

HUMAN EPIDEMIOLOGY AND RESPONSE TO SARS-COV-2 (HEROS)

V3.0/SEPTEMBER 2, 2020

[figure not shown]
NIAID Funding Mechanism: Administrative Supplements to multiple NIAID grants

PROTOCOL CHAIR

[name], MPH

MEDICAL OFFICER

BIOSTATISTICIAN

PROJECT MANAGER

REGULATORY OFFICER

Confidentiality Statement

The information contained within this document is not to be disclosed in any way without the prior permission of the Division of Allergy, Immunology, and Transplantation, National Institutes of Allergy and Infectious Diseases, National Institutes of Health.

National Institute of
Allergy and
Infectious Diseases

Protocol Synopsis

Title	Human Epidemiology and Response to SARS-CoV-2
Short Title	HEROS
Number of Sites	Thirteen US Sites (additional sites may be eventually involved)
Study Primary Objective	Determine the incidence of SARS-CoV-2 infection (via detection of viral RNA in nasal secretions) in children and their household contacts (caregivers and siblings) during the study period.
Study Design	Prospective surveillance for SARS-CoV-2 in children that are currently enrolled in NIH-funded studies (index participant) and their household contacts
Primary Endpoint	The cumulative incidence of SARS-CoV-2 RNA detection in nasal samples among index participants and their household contacts over the study period.
Secondary Endpoint(s)	
 • The percent of index participants and their household contacts with detectable SARS-CoV-2-specific antibodies in serum over the study period. • The cumulative incidence of SARS-CoV-2 detection in nasal samples among index participants with asthma and other atopic disease over the study period as compared to index participants without any atopic disease. • The percent of index participants with asthma and other atopic disease with detectable SARS-CoV-2-specific antibodies in serum over the study period as compared to index participants without any atopic disease. • Changes in the nasal transcriptome that are associated with detection of SARS-CoV-2 in nasal samples among index participants and their household contacts over the study period. • Changes in the nasal transcriptome that are associated with detection of SARS-CoV-2 in nasal samples among index participants with asthma and other atopic disease over the study period as compared to index participants without any atopic disease. • Symptoms (including upper and lower airway, gastrointestinal, and systemic symptom as assessed via questionnaires) that are associated with detection of

	
SARS-CoV-2 in nasal samples among index participants and their household contacts over the study period.
 
 • The cumulative incidence of SARS-CoV-2 detection in nasal samples among index participants using topical, systemic, or inhaled steroids during the study period as compared to index participant that are not using topical, systemic, or inhaled steroids. • The association of baseline demographic and environmental factors or history of bronchiolitis with the cumulative incidence of SARS-CoV-2 detection in nasal samples among index participants and their household contacts over the study period.
Accrual Objective	Up to 2000 families
Study Duration	a minimum of 6 months from time of enrollment to end of study
Inclusion Criteria	
Household members who meet all of the following criteria are eligible for enrollment as study participants:
 
 a. The index participant and/or caregiver understands the study procedures, is willing to conduct them at home, and has the ability to use either a computer or a smart phone to link to and respond to the study questionnaires. If the family does not have access to a computer or a smart phone, they are willing to speak with a study member by phone to answer the questionnaires b. The index participant is 21 years old and younger, lives with caregiver(s), and is or has been a participant in a NIH-funded clinical study from which information on respiratory conditions, including asthma, and other atopic and allergic diseases is available c. The index participant and caregiver will reside in the United States, including Puerto Rico, for the duration of the study d. The index participant will live with the caregiver for at least 50% of the time for the duration of the study e. An English or Spanish speaker is available to serve as the primary contact and as the person who will be responsible for the completion of questionnaires and the collection of study biological samples

	
f. Qualifying siblings must be under 21 years of age and live in the same home as the Index participant and caregiver

Exclusion Criteria	
Individuals who meet any of the following criteria are not eligible for enrollment as study participants:
 
Past or current medical problems, which, in the opinion of the site investigator, may pose risks from participation in the study, may interfere with the participant's ability to comply with study requirements or may impact the quality or interpretation of the data obtained from the study

Study Stopping Rules	
• If protocol continuation poses major new risks to participants or study staff• If, as a result of the COVID-19 pandemic circumstances, protocol feasibility becomes highly questionable

Table of Contents

Glossary of Abbreviations	7
1. Background and Rationale	8
2. Study Objectives	8
3. Study Design.....	9
3.1. Description of Study Design.....	9
3.2. Primary Outcome	10
3.3. Secondary Outcome(s).....	10
3.4. Exploratory Outcome(s)	11
3.5 Randomization	11
4. Selection of Participants and Clinical Sites/Laboratories.....	11
4.2. Rationale for Study Population	11
4.3. Inclusion Criteria	11
4.4. Exclusion Criteria.....	12

COVID-19, the infectious disease caused by SARS-CoV-2, is rapidly affecting humans around the globe. While initial epidemiological data have focused on cases that resulted in severe respiratory disease seen predominantly in adults, little information regarding the infection burden in children is available. This is complicated by the observation that many virologically-confirmed cases in children are asymptomatic (Dong et al, *Pediatrics*, PMID 32179660).

Undocumented, and likely infectious, cases could result in exposure to a far greater proportion of the community than would otherwise occur. Indeed, it has been proposed that undocumented (or silent) infections are the source for almost 80% of documented infections (Li et al, *Science*, PMID 32179701); thus, it is critical to determine the silent and symptomatic infection rate in children. To overcome challenges for clinical study implementation imposed by current healthcare access restrictions, this surveillance study will enroll and prospectively observe eligible children that are current participants in NIH-funded pediatric research studies and their family members. These children and their families are known to study site personnel and because, as part of their participation in the various NIH-funded research studies, most of these children have already been exposed to the procedures that are involved in a surveillance study. This study can therefore be rapidly implemented and realistically conducted remotely without necessitating any visits to a clinical research center.

In addition to the need for surveying children for asymptomatic SARS-CoV-2 infection, this study will allow a comparison between children with asthma and other atopic conditions and children without those conditions. Although, as of the current writing of this protocol, asthma has not been identified as a risk factor for severe COVID-19 disease (Zhang et al, *Allergy*, PMID 32077115), there is evidence that children with asthma and other atopic conditions have increased susceptibility to viral respiratory infections (Esquivel et al, *AJRCCM*, PMC5649984) and that viral respiratory infections may result in worsening of underlying airway disease (Jartti et al, *J Allergy Clin Immunol*, PMID 28987219). No data currently exist as to whether this is true for SARS-CoV-2 infection or whether allergic airway disease could be protective.

2. Study Objectives

2.1 Primary Objective

Determine the incidence of SARS-CoV-2 infection (via detection of viral RNA in nasal secretions) in children and their household contacts (caregivers and siblings) during the study period.

2.2. Secondary Objectives

- a. Determine SARS-CoV-2 antibody development in children and their household members.
- b. Compare SARS-CoV-2 infection status (detection of viral RNA in nasal secretions) and virus-specific antibody development for children with asthma and other atopic conditions (e.g. eczema) versus children without asthma or other atopic conditions.
- c. Determine mucosal immune responses to SARS-CoV-2 infection through gene expression profiling and examine whether these responses are influenced by the presence of asthma or other atopic condition.
- d. Determine whether topical, systemic, or inhaled steroids use, as directed by their care provider, modify the risk of SARS-CoV-2, the severity of infection, or expression of the SARS-CoV-2 receptor.
- e. Determine whether baseline demographic and environmental factors, such as age, sex, race, history of influenza vaccination, rural versus urban living, medications (such as ACE inhibitors), and smoking exposure modify the risk of SARS-CoV-2 infection or the severity of infection.

- f. Assess whether a history of RSV infection or bronchiolitis during infancy modifies severity of SARS-CoV-2 infection.

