2.3. Exploratory Objectives

[figure not shown]
- a. Investigate the transmissibility of SARS-CoV-2 infection among household members.
- b. Investigate whether SARS-CoV-2 infection will be associated with more respiratory symptoms in children with asthma and other atopic conditions, as compared to children without asthma or other atopic conditions.
- c. Investigate whether SARS-CoV-2 infection will be associated with baseline nasal microbiome or with changes in the nasal microbiome and whether the underlying atopic status plays a role in this relationship.
- d. Investigate whether SARS-CoV-2 infection, as identified by the presence of virus in nasal secretions, will be associated with the presence of virus in stool.
- e. Determine whether IgA antibody specific for common coronaviruses (229E, OC43, NL63, HKU1) in the blood at baseline modifies the risk of SARS-CoV-2 infection or the severity of infection.
- f. Investigate earlier SARS-CoV-2 exposure by assaying historical samples from enrolled participants.
- g. Identify protective/risk factors for disease acquisition integrating all available data using machine learning approaches and network analysis to provide efficient representation of complex interactions.

3. Study Design

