3.3. Secondary Outcome(s)

- a. The percent of index participants and their household contacts with detectable SARS-CoV-2-specific antibodies in serum over the study period.
- b. The cumulative incidence of SARS-CoV-2 detection in nasal samples among index participants with asthma and other atopic disease over the study period as compared to index participants without any atopic disease.
- c. The percent of index participants with asthma and other atopic disease with detectable SARS-CoV-2-specific antibodies in serum over the study period as compared to index participants without any atopic disease.
- d. Changes in the nasal transcriptome that are associated with detection of SARS-CoV-2 in nasal samples among index participants and their household contacts over the study period.
- e. Changes in the nasal transcriptome that are associated with detection of SARS-CoV-2 in nasal samples among index participants with asthma and other atopic disease over the study period as compared to index participants without any atopic disease.
- f. Symptoms (including upper and lower airway, gastrointestinal, and systemic symptom as assessed via questionnaires) that are associated with detection of SARS-CoV-2 in nasal samples among index participants and their household contacts over the study period.
- g. The cumulative incidence of SARS-CoV-2 detection in nasal samples among index participants using topical, systemic, or inhaled steroids during the study period as compared to index participant that are not using topical, systemic, or inhaled steroids.
- h. The association of baseline demographic and environmental factors or history of bronchiolitis with the cumulative incidence of SARS-CoV-2 detection in nasal samples among index participants and their household contacts over the study period.

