3.4. Exploratory Outcome(s)

- a. Symptoms associated with detection of SARS-CoV-2 in nasal samples.
- b. Nasal microbiome outcomes of alpha and beta diversity among index participants and their household contacts with detectable SARS-CoV-2 in nasal samples over the study period.
- c. The percent of participants with symptomatic SARS-CoV-2 infection in whom the virus can be detected in stool.
- d. Levels of IgA antibodies specific for common coronaviruses (229E, OC43, NL63, HKU1) in the blood at baseline.
- e. The percent of index participants with detectable SARS-CoV-2-specific antibodies in samples that were collected and stored prior to the current study period.

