10.2 Definitions

10.2.1 Adverse Event

For this surveillance study, an adverse event (AE) is defined as any untoward or unfavorable medical occurrence in a participant that is associated with a study procedure mandated by the protocol and occurs within 48 hours of this procedure. This definition excludes all untoward or unfavorable medical occurrences not related to a study procedure, including hospitalizations or deaths. The study mandated procedures are listed in the Schedule of Events (Table A). Criteria for determining the relatedness of an AE to a study procedure and grading its severity are provided in Sections 10.3.1 *Grading Criteria* and 10.3.2 *Attribution Definitions*. The worsening of a participant's pre-existing medical condition will not be considered an AE unless the worsening is related to a study mandated procedure.

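### Severity, nasal–stool and baseline-microbiome objectives have no listed outcome that can answer them

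*Combined protocol and SAP*

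**What the plan says.** **Severity.** Section 2.2f sets the objective "Assess whether a history of RSV infection or bronchiolitis during infancy modifies severity of SARS-CoV-2 infection". Sections 2.2d (steroid use), 2.2e (demographic and environmental factors) and 2.3e (IgA to common coronaviruses) also name severity of infection. Bronchiolitis appears in one outcome, 3.3h: "The association of baseline demographic and environmental factors or history of bronchiolitis with the cumulative incidence of SARS-CoV-2 detection in nasal samples". The nearest outcome to severity is 3.3f: "Symptoms (including upper and lower airway, gastrointestinal, and systemic symptom as assessed via questionnaires) that are associated with detection of SARS-CoV-2". Outcome 3.4a is a shorter statement of the same idea.

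**Stool.** Objective 2.3d asks whether virus in nasal secretions is associated with virus in stool. The stool outcome, 3.4c, is "The percent of participants with symptomatic SARS-CoV-2 infection in whom the virus can be detected in stool".

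**Microbiome.** Objective 2.3c is "Investigate whether SARS-CoV-2 infection will be associated with baseline nasal microbiome or with changes in the nasal microbiome", and it goes on to ask whether atopic status plays a role. The outcome, 3.4b, is "Nasal microbiome outcomes of alpha and beta diversity among index participants and their household contacts with detectable SARS-CoV-2 in nasal samples".

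**Analysis and data.** Section 11.2 gives Kaplan-Meier curves for detection, attack rates, and a Cox model for time to antibodies. It has no analysis of severity, stool or microbiome. On the data side, stool swabs are taken from all enrolled participants from Week 2 (6.2.1), and all are tested by RT-qPCR (section 7). Symptom and exposure surveys run every 2 weeks (6.2.2). Leftover RNA and DNA from all nasal swabs are stored for possible uses that include the microbiome (section 7).

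**The concern.** An objective can be met only if some outcome measures the quantity it asks about, in the people needed for the comparison. Three gaps stand out.

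- Whether a child is infected and how ill an infected child becomes are different quantities with different denominators. If 3.3h is all that is reported on bronchiolitis, objective 2.2f is left unanswered, or a result on incidence is read as a result on severity. If severity is defined only after the data are seen, the cut-points can follow the results.
- A percentage in one group is not an association. Under 3.4c, nobody with a negative nasal swab enters the calculation, and neither does anyone infected without symptoms. Section 1 treats silent infection as critical to measure.
- Among participants who all become infected, the baseline microbiome cannot be related to becoming infected, because infection does not vary.

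**Working it through.** **Step 1: each objective against the closest outcome.**

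| Objective | Quantity asked for | Closest outcome | What the outcome gives |
|---|---|---|---|
| 2.2f | Severity given infection, by RSV or bronchiolitis history | 3.3h; 3.3f and 3.4a | 3.3h: incidence by bronchiolitis history, RSV not named. 3.3f and 3.4a: symptoms by detection, with no grade and no split by history |
| 2.2d, 2.2e, 2.3e (severity parts) | Severity by steroid use, baseline factors, IgA | 3.3g, 3.3h, 3.4d | Incidence (3.3g, 3.3h) or baseline IgA levels alone (3.4d) |
| 2.3d | Stool positivity, nasal-positive versus nasal-negative | 3.4c | Stool positivity in symptomatic infected participants |
| 2.3c, baseline | Baseline microbiome, later infected versus not | 3.4b | Diversity in the infected only |
| 2.3c, change and atopy | Change around infection; difference by atopy | 3.4b | The right people, but neither contrast is stated |

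**Step 2: why the gap is structural.**

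- *Severity.* 3.3h estimates P(detected | history). Objective 2.2f needs P(severe | detected, history). If history leaves the risk of infection unchanged but worsens the illness, 3.3h shows no association.
- *Stool.* Let a and b be stool-positive and stool-negative counts among nasal-positive participants, and c and d the same among nasal-negative participants. The association needs a/(a+b) and c/(c+d), or the odds ratio ad/(bc). Outcome 3.4c gives only a/(a+b), and only for the symptomatic part of that row. Nothing supplies c and d.
- *Baseline microbiome.* In the 3.4b population P(infected) = 1 at every baseline value, so no association can be estimated.

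**Step 3: numbers available for severity.** Section 11.3 uses n = 2000 and Wilson intervals,

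(p + z²/2n ± z√[p(1−p)/n + z²/4n²]) / (1 + z²/n), with z = 1.96.

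| Incidence | Recomputed 95% CI | Section 11.3 | Infected index children |
|---|---|---|---|
| 3% | 2.34–3.84% | 2.3–3.84% | 2000 × 0.03 = 60 |
| 5% | 4.13–6.04% | 4.1–6.0% | 2000 × 0.05 = 100 |
| 10% | 8.76–11.39% | 8.7–11.4% | 2000 × 0.10 = 200 |
| 20% | 18.31–21.81% | 18.3–21.8% | 2000 × 0.20 = 400 |

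The plan's figures are reproduced to within 0.1 point. They describe incidence in 2000; severity can be seen only in the last column.

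**Step 4: illustration of precision.** The documents give no severity figures, so these are assumptions: 20% severe without the history, and 10% to 50% of infected children with the history. Power is 80% at two-sided 0.05, from

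Φ[(|p₂−p₁| − 1.96·SE₀)/SE₁], with SE₀ pooled and SE₁ unpooled.

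Example: 60 infected, 10% with the history, so n₁ = 54 and n₂ = 6. With p₁ = 0.20 and p₂ = 0.727, the pooled proportion is 0.2527, SE₀ = 0.187 and SE₁ = 0.190. The argument is (0.527 − 0.367)/0.190 ≈ 0.845, and power is 0.80.

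| Infected | 95% CI if 50% are severe | Smallest detectable severe % with the history |
|---|---|---|
| 60 | 37.7–62.3% | 54–73% |
| 100 | 40.4–59.6% | 46–61% |
| 200 | 43.1–56.9% | 38–49% |
| 400 | 45.1–54.9% | 32–40% |

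The normal approximation is rough in the smallest cells. Household contacts would add infected participants, but the documents do not give their number.

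**The case against.** The strongest replies are these.

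- **Symptoms are already an outcome.** 3.3f covers airway, gastrointestinal and systemic symptoms by questionnaire, and in a home-based cohort this is close to severity. That stands as far as the data go. It does not supply a grade or a comparison by RSV or bronchiolitis history.
- **The protocol does not pair objectives with outcomes.** A reader might infer that bronchiolitis severity is to be measured as incidence. The documents do not say so; 3.3h may simply be a further incidence outcome. What they support is that no listed outcome serves 2.2f.
- **The microbiome outcome is not without any comparison.** A reader might infer that 3.4b allows none. With swabs every 2 weeks, infected participants can supply their own pre-infection samples, and atopic can be compared with non-atopic within the infected. Only the baseline part of 2.3c strictly needs uninfected participants.
- **Adverse event reporting.** Section 10.2.1 says "This definition excludes all untoward or unfavorable medical occurrences not related to a study procedure, including hospitalizations or deaths". A reader might infer that hospitalisation for COVID-19 is not recorded at all. That sentence limits safety reporting to study procedures. It does not show what the questionnaires ask, and their content is not in the documents.
- **Priority.** The stool and microbiome items are exploratory. That stands, and it limits their weight.

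**Conclusion.** The point holds. Four objectives name severity, three of them secondary, and no outcome grades it. Outcome 3.4c cannot estimate the nasal–stool association and leaves out asymptomatic infection. Outcome 3.4b cannot answer the baseline part of 2.3c, and it leaves the change and atopy contrasts unstated.

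The defect lies in the outcome definitions. It would be too strong to conclude that the data are not collected: stool results, surveys and stored nasal material are already planned for everyone enrolled.

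In size, about 60 to 400 index children would be available for severity at 3% to 20% incidence, and only large differences would be detectable at the lower end. That rests on full enrolment of 2000 and, for the detectable differences, on the assumptions in step 4. The matching of objectives to outcomes is by content, but no other listed outcome fits better.

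The primary endpoint is unaffected. The change should be made before the data are analysed, with the severity outcome first in priority.

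**What to change.** 1. **Stool (3.4c).** Redefine as stool RT-qPCR positivity compared between nasal-positive and nasal-negative participants at matching time points, using all scheduled and illness stool swabs. Report symptomatic and asymptomatic infection separately, and allow for clustering within households. Restricting the comparison to illness events would keep the present omission of silent infection.

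2. **Severity (new outcome).** Define an ordinal severity outcome from the existing symptom surveys for all RNA-positive participants, with its levels fixed before results are seen. If the surveys record care sought or hospitalisation, place these above the illness threshold rather than merging them with it. Compare by RSV and bronchiolitis history, and by the factors in 2.2d, 2.2e and 2.3e. Account for detection route, scheduled or illness-triggered swab, and give a scheduled-swab-only analysis as a sensitivity analysis. It should not be the main one: illness swabs are taken because the threshold was met, so dropping infections first found on them would deplete the top level. State that precision is limited to the infected.

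3. **Microbiome (3.4b).** Compare baseline diversity between participants who become RNA-positive and those who remain RNA-negative, and add within-person change from the pre-infection swab, both by atopic status.

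**Cost.** Items 1 and 2 need revised wording and some added analysis, with no new samples or assays. Item 3 may need sequencing of some stored swabs from RNA-negative participants. At the incidences above, 1600 to 1940 index children (2000 − 400 to 2000 − 60) could serve as comparators, so a sample of them can be drawn to contain the cost.
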